Pre-intervention	Parent completes: HAM-A	2 minutos
		3 minutes
	PHQ-9	3 minutes 3 minutes
	ADCS (ADAPTED PACS) DERS	5 minutes
	DBT-WCCL	5 minutes
	WACB	3 minutes
	CBCL	10 minutes
	ERC	5 minutes
	PSI	7 minutes
	PSOC	5 minutes
	PS	7 minutes
	CCNES	8 minutes
		Total: 64 minutes
₽		
Treatment Phase	Parent completes weekly	
(20 assessment time points)	measures:	5 minutos
20-weekly sessions of DBT Skills +PT		5 minutes
	DBT-WCCL ERC	5 minutes 5 minutes
	WACB	3 minutes
	PS	7 minutes
	CCNES	8 minutes
	Skill Use Diary Card	5 minutes
		Total for Weekly Assessment: 38 minutes
	Parent participates in weekly	2.5 hours/week
	DBT Skills +PT sessions +	
	individual check ins (10-15 min)	
	when necessary as part of	

	standard clinical case management	Total: 190 minutes/week
₽		
Post-intervention	Parent completes: HAM-A PHQ-9 ADCS (ADAPTED PACS) DERS DBT-WCCL WACB CBCL ERC PSI PSOC PS CCNES CSQ-8 Qualitative exit interview (including SCID 5 diagnostic assessment of current substance use disorder)	3 minutes 3 minutes 3 minutes 5 minutes 5 minutes 3 minutes 5 minutes 5 minutes 5 minutes 5 minutes 8 minutes 5 minutes 60 minutes Total: 129 minutes

Procedures

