increase positive interactions and use parental attention to reward positive behavior, how to set up a reward system, how to use effective commands, how to use consequences to discourage negative behavior, and how to teach children problem solving. Emotion coaching (EC) portions of the intervention cover: psychoeducation on children's emotional development, how to teach children to identify and label emotions, how to validate children's emotions, handling children's negative emotions, fostering children's positive emotions and how parents can model emotion regulation and expression to their children.

Post-intervention Assessment. Following the 20-week intervention, parents will be asked to complete the set of measures listed in Fig. 1: Study Phase: *"Post-intervention"* via online Qualtrics questionnaires. In addition, they will participate in an exit interview (approximately 1 hour), conducted over Zoom by a trained staff member who was not one of the DBT Skills +PT co-leaders. During the exit interview,

parents will be assessed for any current (since the clinical intake) substance use disorder using the SCID 5. Additionally, parents will be asked to share their thoughts and experiences from participating in the DBT Skills +PT group intervention.

Materials. All measures are well-validated, and have been used with clinical samples, in samples with racial and ethnic diversity, and in intervention studies which demonstrate change. Figure 1 provides a summary of the data collection schedule and measures, which are briefly outlined below in the order in which they appear in Figure 1. This broad battery of assessments is necessary to achieve the study aims, which include evaluating changes in three related domains (parent symptoms, parenting behaviors, and child symptoms), and comparing these changes to the clinical trial literature bases for DBT, PMT and EC (which have often utilized different measures to assess treatment-induced changes). All self and parent-report measures are included in this submission (see Appendices H-T).

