Aim 1. Determine feasibility, acceptability and implementation. Three types of feasibility will be examined. Feasibility of recruitment will be assessed by examining the number of participants meeting eligibility on the initial online screener and the number of participants meeting eligibility following the clinical intake. Feasibility of measurement tools will be assessed by calculating the average time taken by participants to complete the online Qualtrics questionnaires, and the average percentage of missing data from the online questionnaires. Feasibility of the intervention will be evaluated by calculating the average number of sessions attended by parents.

Acceptability will be examined by averaging the total scores obtained from the Client Satisfaction Questionnaire (CSQ-8). In addition, using qualitative thematic analyses, we will report on data collected during the exit interview, identifying overall themes about the intervention that emerge from parents' comments.

We will examine implementation by calculating the average daily number of DBT and parenting skills parents report using each week on their diary card (averaged across parents) and comparing these to skill use reported in other published research (ex. 7-8 DBT skills per week; Gamache [name] et al., 2017). We will primarily report data for Aim 1 at an aggregated group level. We may also include de-identified information at the individual level in the form of quotes from parents' exit interviews.

Aim 2. Evaluate pre-post and weekly changes. We will examine pre-post changes for the primary outcomes of DBT Skill use (DBT-WCCL), parental emotion dysregulation (DERS), parenting stress (PSI) and parenting quality (PS, CCNES). Pre-post change scores will also be calculated for the secondary outcomes of child internalizing and externalizing behaviors (CBCL), child emotion regulation (ERC), parent mental health symptoms (HAM-A, PHQ-9, ADCS). Pre-post change scores will be compared to the clinical trial literature base for DBT and parent training interventions which often use the same measures and for which expected change scores are established. Additionally, based on post-intervention reports during the SCID 5 diagnostic interview, the percentage of parents reporting sustained recovery (vs relapse) from substance use disorder will be calculated and reported.

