We will examine change across time based on data available in the weekly assessment measures of parents' DBT and parenting skill use (DBT-WCCL, Skill Use Diary Card), parents' emotion dysregulation (DERS), parenting quality (PS), and children's symptoms and behaviors (ERC and WACB). Consistent with common practice in case study designs (Kazdin, 2003; Kazdin, 2019; Rizvi & Nock, 2008), we will primarily use visual inspection (i.e. evaluating graphical displays of participants' weekly scores) to examine the data collected during Weeks 1-20 of the DBT Skills +PT intervention. We will use the same procedures to examine changes in data collected at the four time points representing the start of each DBT module. We will inspect several aspects of these data, such as changes in the trajectories of each measure, to determine the direction and extent of change in the measured symptoms and behaviors from week to week, and the timing of when those changes occurred. We will also characterize the order in which changes unfold over time (e.g. increased DBT skill use precedes improvement in parent emotion regulation, which precedes improvements in parenting quality measures, which precedes improvements in child behavior measures). These visual inspection analyses will be conducted at both the individual level and at an aggregated group level.

We will employ a number of standard methods of statistical analysis of single-case experimental design (SCED) data to further examine, quantify and corroborate results of visual inspection. Consistent with previous SCED studies, we will calculate Tau-U effect sizes (Parker et al., 2011; Vannest & Ninci, 2015; Brossart et al., 2018), linear regressions (Ramaiya et al., 2018) and perform hierarchical linear modeling which can be used to aggregate single-case results (Van den Noortgate & Onghena, 2007; Ugille et al., 2012). These analyses will provide preliminary information on the rate and order of change for the different targeted symptoms and behaviors, and enable us to report on the degree to which DBT Skills +PT changed parent-reported symptoms and behaviors at the level of individual parents as well as at the group level, aggregating data across all participating parents.

D. Research Population & Recruitment Methods

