Compensation/Reimbursement. Participating families who are eligible for the full study can be compensated up to \$360 for their participation in the study. Payments will be made after participants complete each phase of the study and are broken down as follows: \$60 after the intake, \$30 after the pre-intervention assessment, \$10 after each weekly measure they complete during the 20 weeks of treatment, \$30 after the post-intervention assessment, and \$40 after the exit interview. Compensation will be provided via check payments which will be mailed to participants or via reloadable debit cards that will be provided to them. Potential costs to the participants include childcare expenses during the clinical intake, the assessments, intervention sessions and the qualitative exit interview.

Attrition. Efforts to minimize attrition include provision of incentives (which calculated across time spent on assessments are estimated to be in excess of \$20/hour for those participating in the full study). Furthermore, the case study design, which does not necessitate inferential statistical analyses, ensures that our research aims can still be accomplished despite participant attrition.

E. Informed Consent Process

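### The absence of inferential tests does not protect the aims from attrition: post-intervention results rest only on the parents observed, and the plan gives no denominator or unknown category for recovery

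*Combined protocol and SAP*

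**What the plan says.** Section D, Attrition, rests its assurance on the design, which "does not necessitate inferential statistical analyses, ensures that our research aims can still be accomplished despite participant attrition".

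The results that need an observation after the 20 weeks are set out in section C:

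- **Recovery.** At the exit interview "parents will be assessed for any current (since the clinical intake) substance use disorder using the SCID 5", and under Analyses, Aim 2, "the percentage of parents reporting sustained recovery (vs relapse) from substance use disorder will be calculated and reported".
- **Acceptability.** "Acceptability will be examined by averaging the total scores obtained from the Client Satisfaction Questionnaire (CSQ-8"), which Figure 1 lists at post-intervention only. Themes from the exit interview are the second source.
- **Pre-post change.** The primary outcomes are DBT-WCCL, DERS, "parenting stress (PSI) and parenting quality (PS, CCNES"). The secondary outcomes are CBCL, ERC, HAM-A, PHQ-9 and ADCS. Section B, Aim 2, defines this change by two time points and sets the aim across all enrolled parents.

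The only missing-data provision in the main text is a feasibility measure, "the average percentage of missing data from the online questionnaires". Section D, Participants, plans to enrol up to 15 parents so that 12 attend at least 4 of the 20 sessions.

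**The concern.** The reason given does not support the conclusion. A descriptive mean or percentage is computed from the people observed, just as an inferential one is, and selective loss can shift either.

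The plan expects to lose some parents, yet it does not say over whom recovery is calculated, how parents of unknown status are shown, or whether those who stop attending are still asked for the post assessment. The retention target does not help: a parent counted towards the 12 may have attended only 4 sessions and need not be seen after week 20.

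The results have two onward uses. Pre-post change is to be compared with the trial literature, and the pilot is presented as groundwork for a larger randomized trial. Both uses depend on knowing how many of the enrolled parents each figure represents.

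**Working it through.** **1. The plan's own figures.** Three groups of 4 to 5 parents give 12 to 15, which agrees with 15 enrolled and a target of 12. The implied loss is (15 − 12)/15 = 20%, but no attrition rate is stated, so this is back-calculated. It concerns reaching 4/20 = 20% of sessions, not being assessed after week 20.

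**2. What each result needs.**

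| Result | Needs | Effect of a parent with no post assessment |
|---|---|---|
| Recruitment counts, attendance | Study records | None |
| Individual weekly series | Weekly questionnaires | Kept up to exit |
| Group weekly displays, module comparisons, order of change | Weekly data through later modules | An early leaver drops out part-way and the group's composition changes |
| Recovery, CSQ-8, exit-interview themes | Post-intervention contact | Contributes nothing |
| Pre-post change, all 10 measures | Both time points | Contributes nothing |

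No rule lets a last weekly score stand in for the post score, so the final row covers all ten measures, including those also collected weekly. The third row matters because section B expects child behaviour to improve last.

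**3. Which measures have a weekly series to show instead.** Figure 1, Treatment Phase, has seven entries: DERS 5, DBT-WCCL 5, ERC 5, WACB 3, PS 7, CCNES 8 and diary card 5. The first label is not legible in the text available; DERS is taken from the Aim 2 weekly list. The sum is 5+5+5+3+7+8+5 = 38, which matches "Total for Weekly Assessment: 38 minutes".

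On Figure 1, the pre-post measures with no weekly value are PSI, CBCL, HAM-A, PHQ-9 and ADCS. That is 5 of 10: 1 of 5 primary and 4 of 5 secondary.

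CCNES is not settled. Figure 1 includes it, and without it the weekly total would be 38 − 8 = 30 minutes. But section C, under the DBT Skills +PT intervention, speaks of five weekly measures. The Aim 2 weekly analysis names DBT-WCCL, the diary card, DERS, "parenting quality (PS), and children's symptoms and behaviors (ERC and WACB"). That is five questionnaires plus the diary card, with CCNES absent. If CCNES is not weekly, the count is 6 of 10, with 2 of 5 primary.

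**4. Illustration for recovery.** Let N = 15 be enrolled and u be of unknown status, and assume 2 observed parents have a disorder. Then n = 15 − u are observed and x = n − 2 have no disorder. The observed percentage is x/n, the bounds over all enrolled are x/15 to (x + u)/15, and the width is u/15.

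| u (assumed) | Observed | All-enrolled bounds | Width, points |
|---|---|---|---|
| 1 | 12/14 = 85.7% | 80.0–86.7% | 6.7 |
| 2 | 11/13 = 84.6% | 73.3–86.7% | 13.3 |
| 3 | 10/12 = 83.3% | 66.7–86.7% | 20.0 |
| 6 | 7/9 = 77.8% | 46.7–86.7% | 40.0 |

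No size can be given for CSQ-8 or pre-post change, because the plan supplies no means or standard deviations.

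**The case against.** The strongest defence is that this is a descriptive pilot of 12 to 15 parents, and results among those assessed can be reported whatever the attrition. The plan also takes steps against loss. It intends an exit interview with every parent and does not restrict the post battery to attenders. It enrols more parents than the target, obtains permission to contact by email, text and phone, has a family with two eligible parents choose the one likelier to finish, and pays $30 + $40 = $70 for the post battery and interview. Stating the n behind each mean is routine reporting.

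Most of this stands, and it limits the severity. It does not make the assurance true, and it does not supply a denominator or an unknown category for recovery.

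Three stronger readings are tempting and not supported:

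- **That leaving the group means being lost.** The plan does not say so. The exit SCID 5 looks back to intake, so a leaver who is interviewed still supplies recovery status. The loss is confined to parents who are not reached or who decline.
- **That recovery will be overstated.** This is plausible if relapse makes a parent harder to reach, but nothing in the documents shows it.
- **That a stated aim fails.** Recovery is an added descriptive result under the Aim 2 analyses and is not named in the Specific Aims. For PSI and CSQ-8, which do serve the aims, no size of effect can be shown.

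A reader might also infer that the measures collected weekly escape the problem. They do not: without a post score there is no pre-post change on them either.

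**Conclusion.** The sentence claims a property that the design does not have. Only recruitment and attendance counts are assured whatever the attrition. Individual weekly series hold up to exit; group-level weekly results and everything measured after week 20 rest on the parents observed. Five of the ten pre-post measures, or six if CCNES is not weekly, have no weekly series to fall back on, and PSI is a primary outcome in either case.

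The firm quantity is the width of the recovery bounds: 6.7 points per parent of unknown status among 15 enrolled. The numbers unreached and the two observed disorders are assumed. It is also assumed that weekly questionnaires stop when a parent leaves, which the plan does not state. The appendices, including the consent form, and part of section I were not available and could contain relevant provisions.

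Severity is minor to moderate: one over-strong sentence and a reporting gap, in a descriptive pilot whose figures are meant to inform a larger trial.

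**What to change.** 1. In section D, Attrition, replace the assurance with a statement that only recruitment and attendance counts are unaffected by attrition and that all other results rest on the parents observed. Limiting it to the weekly displays would not be enough, since those also lose leavers.
2. Confirm that the post battery and exit interview are sought from every enrolled parent, including those who stopped attending.
3. Report recovery over all enrolled parents as no disorder, disorder or unknown, with best- and worst-case bounds.
4. Give the number of parents behind the CSQ-8 mean, the interview themes and each pre-post mean. Where weekly data exist, show leavers' series up to exit beside the pre-post means.
5. Reconcile Figure 1, the intervention procedures and the Aim 2 weekly analysis on whether CCNES is collected weekly. If it is, add it to that analysis.

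The cost is mostly wording, some effort to contact leavers, and one extra display if CCNES is weekly. Payments of $70 per leaver ($210 for three, $420 for six) already fall within the planned maximum per parent of 60 + 30 + 20×10 + 30 + 40 = $360. The downside is that some leavers will still not be reached, and the recovery figures may look wider or less favourable.

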Following this, parents will complete a demographic questionnaire, the Peabody Picture Vocabulary Test-V (PPVT-V Q-Global), the Patient Health Questionnaire for Depression (9-items; PHQ-9), and the Structured Clinical Interview for DSM-5 (SCID 5). Parents will be ineligible to participate if they meet for the exclusionary criteria detailed in section D. Research Population & Recruitment Methods: Participants.

Pre-intervention Assessment. Parents who meet criteria for the study following the clinical intake will be asked to complete a broad battery of questionnaires (see Fig 1. Study Phase: *"Pre-intervention"*) to assess parent mental health symptoms, parenting stress, parenting quality and child mental health symptoms. The questionnaires will be completed online via UO Qualtrics and parents will receive an encrypted email (i.e. Hushmail) from the project coordinator with the UO Qualtrics link.

DBT Skills +PT intervention. The study plans to recruit three groups of approximately 4-5 parents/group. Parents will be recruited twice throughout the course of the year to facilitate running up to three groups (see section D. Research Population & Recruitment Methods for more details). Once a group of parents has been recruited, participants will take part in 20 weekly DBT Skills +PT intervention sessions. The group sessions are conducted remotely over a HIPAA compliant version of Zoom and groups are led by [name] (PI) and three other doctoral level student co-leaders who are supervised by [name], a licensed clinical psychologist who is trained in both DBT and parent training. [name] [name] (Co-I) and [name] (Faculty Advisor) may also be consulted and provide supervision, when needed.

Prior to the start of the first session, co-leaders will conduct 1 hour individual orientation sessions over Zoom with each participating parent, in order to orient them to the intervention, review intervention related portions of the consent form, and provide participating parents with an opportunity to ask questions in private if they wish.

Before each weekly session, parents will receive an encrypted email from the project coordinator asking them to complete the 5 measures listed in Fig. 1: Study Phase: "Treatment Phase", via a set of online UO Qualtrics questionnaires.

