- P. The Coping with Children's Negative Emotions Scale (CCNES; Fabes, Eisenberg & Bernzweig, 1990) assesses parental self-report of emotion socialization practices. Parents are presented with 12 vignettes describing scenarios in which their children exhibit distress. Parents rate (on a Likert scale of 1-7) the likelihood they would engage in 6 potential parental responses to these situations, with each corresponding to 6 subscales: distress reactions, punitive reactions, minimization, expressive encouragement, emotion-focused reactions and problem-focused reactions. The first three can then be summed into an Invalidating/Unsupportive composite and the latter three can be summed into a Validating/Supportive composite.

- Q. Skill Use Diary Card. A diary card developed for this study will be used to assess parents' weekly use of specific DBT and parenting skills, both as a study measure of treatment dosage and for treatment purposes. Parents are asked to circle days of the week in which they used each skill. Additionally, they are asked if DBT Skills were used in a parenting or a non-parenting context. Diary cards also include an additional question that assesses for suicidal thoughts over the past week.
- R. The Client Satisfaction Questionnaire (CSQ-8; Attkisson & Zwick, 1982) will be used to assess acceptability of the intervention. It is a brief 8-item self-report measure in which clients are asked to rate (on a Likert scale of 1-4) their satisfaction with the intervention.
- S. Qualitative Exit Interview. A semi-structured exit interview will be used to evaluate parents' satisfaction with the intervention, challenges they experienced completing the intervention, their use of DBT/Parent training skills, and suggestions they have for improving the intervention delivery. Interviews will be video recorded so that representative quotes and themes can be identified.

Analyses

We will conduct multiple analyses to evaluate how, when, why, and to what extent the DBT Skills +PT intervention was effective in changing parents' mental health and/or parents' parenting quality and/or children's mental health and behavior. All data will be de-identified and all findings from our analyses will be reported anonymously.

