A single informed consent form (see Appendix A. Informed Consent Form) will cover all phases of the study (clinical intake, pre-intervention assessment, intervention, and post-intervention assessment). Prior to the clinical intake, a copy of the Informed Consent Form will be emailed to participants. At the start of the clinical intake, a trained research staff member will give each parent an overview of the study in its entirety and review confidentiality practices, potential risks, and any benefits. Participants will also be informed that as this is an intervention development project, the intervention group coleaders are involved in the research and will have access to assessment data. Limits to confidentiality will be covered (as in the case of abuse of vulnerable populations, harm to self or others), as will the steps that will be taken if this information is revealed. Because the clinical intake and the assessments will specifically ask about suicidality, parents will be told in detail what procedures will occur if they are judged to be a risk to themselves or others (see Appendix X. Critical Risk Protocol). Parents will be invited to ask questions and will then provide consent via electronic signature on the Informed Consent Form and email it back to the staff member conducting the clinical intake.

At the start of the post-intervention qualitative interview, the trained research staff member conducting the interview will briefly cover the purpose of the exit interview and review the relevant portion of the consent form with the parent. Parents will be asked to verbally reaffirm their consent to participate. We will clearly track that the parent's consent to participate in the study was collected at the clinical intake and at the post-intervention exit interview (see Appendix Z. Documentation of Informed Consent).

A copy of the informed consent form will be posted on a Federal website (e.g. clinicaltrials.gov) after the study is closed to recruitment and no later than 60 days after the last study visit by any subject.

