Roles and Research Duties. The principal investigator ([name]) and faculty advisor ([name]) will be involved in all aspects of this research. The co-Investigator ([name]) will help in the development and refinement of intervention session plans and will be highly involved in preparing resultant manuscripts from this study. The clinical supervisor ([name]) will provide supervision for all intervention coleaders by reviewing video recordings of sessions and meeting with co-leaders regularly to provide clinical feedback. The project coordinator will be involved in the development of recruitment materials, recruitment efforts, scheduling, data collection, data storage and following of procedures for this protocol. [name] (PI) will train all research assistants who may be involved in qualitative coding of the exit interviews. In addition, [name] and the additional co-leaders will be responsible for conducting clinical intakes and co-leading the DBT+PT intervention. A trained clinical psychology graduate student will be responsible for conducting the exit interviews.

Training and Oversight. [name] (PI), the other group co-leaders and [name], will participate in weekly consultation meetings. These consultation team meetings are designed to assist co-leaders in adhering to the DBT treatment model and the Parent Training manual. All research personnel involved in recruitment, screening, intakes, assessments and the intervention will complete the Collaborative Institutional Training Initiative's (CITI) Protection of Human Research Subjects program for Social-Behavioral-Educational Researchers as well as the Good Clinical Practices training to ensure ethical and professional conduct of the research. Study personnel will complete and have up-to-date CITI training certificates on file with the Project Coordinator. Additionally, each member of the study team will be trained by the PI to follow the approved research protocol.

Appendices submitted with this application

- A. Informed Consent Form
- B. Recruitment Email
- C. Craigslist Posting
- D. Facebook Posting
- E. Online Screening Script
- F. Intake Scheduling Script
- G. Difficulties with Emotion Regulation Scale (DERS)
- H. CAGE-AID Screener
- I. Demographic Questionnaire
- J. Patient Health Questionnaire 9 (PHQ-9)
- K. Hamilton Anxiety Rating Scale (HAM-A)
- L. The Aggregated Drug Craving Scale (ADCS)
- M. DBT Ways of Coping Checklist (DBT-WCCL)

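### Parents are told that their group co-leaders can see assessment data and the CSQ-8 is not exempted, so the acceptability score carries an avoidable risk of upward bias

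*Combined protocol and SAP*

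**What the plan says.** Section E (Informed Consent Process) describes what parents hear at the clinical intake, including that "the intervention group coleaders are involved in the research and will have access to assessment data". The same section lists the post-intervention assessment among the phases covered by the consent form and sets no measure apart.

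Figure 1 places the CSQ-8 in the post-intervention phase ("PSI PSOC PS CCNES CSQ-8 Qualitative exit interview"). Under Post-intervention Assessment in section C, "parents will be asked to complete the set of measures listed in Fig. 1: Study Phase" is the instruction for that phase, with completion through Qualtrics. Materials, item R, describes an 8-item instrument on which "clients are asked to rate (on a Likert scale of 1-4) their satisfaction with the intervention".

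The analysis for Aim 1 reads: "Acceptability will be examined by averaging the total scores obtained from the Client Satisfaction Questionnaire (CSQ-8". It adds a thematic analysis of the exit interview. It gives no comparator, benchmark or threshold for the CSQ-8.

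The groups are led by the PI and "three other doctoral level student co-leaders" (section C, DBT Skills +PT intervention). Roles and Research Duties (section I) says the PI "will be involved in all aspects of this research".

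Section F has questionnaires labelled with an ID number only. The list linking IDs to names is held apart for key study personnel, and the stored questionnaire data are open to the research team. The exit interview, by contrast, is "conducted over Zoom by a trained staff member who was not one of the DBT Skills +PT co-leaders".

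**The concern.** A satisfaction rating is most useful when the rater has no reason to please the person being rated. Here parents have spent up to 20 weeks in a small group with the co-leaders and were told at the outset that those co-leaders would have access to what they report. Some may score more generously than they would in private.

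Acceptability is a named part of Aim 1, and the pilot is meant to lay the ground for a larger randomized trial. If the mean CSQ-8 is inflated, the intervention will look more acceptable than it is, and problems that would affect retention in the larger trial may go unnoticed. The usual reason for therapist access, clinical monitoring during treatment, does not extend to a satisfaction score collected after the intervention has ended.

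**Working it through.** The protocol states no CSQ-8 target, SD, error rate or power figure, so there is no figure of its own to reproduce. The check is a chain of readings followed by one illustration.

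**Does the access statement reach the CSQ-8?**
- Section E: co-leaders have access to assessment data, with no exception.
- Section E also names the post-intervention assessment as a study phase.
- Figure 1 and Post-intervention Assessment put the CSQ-8 in that phase.
- So the CSQ-8 is covered. This is an inference, but no other passage in the supplied text points the other way.

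**Do other provisions close the gap?**
- *ID coding (section F).* It hides names on the questionnaire. However, key study personnel hold the link, co-leaders are not excluded from that group, and the PI is a co-leader. With about 4-5 parents per group, an ID gives limited cover. The bias also depends on what parents believe, and they have been told of the access.
- *Online completion after treatment (section C).* Nobody is present when the parent answers, and treatment is over. This lowers the pressure but does not change who can read the answer.
- *Exit interviewer who is not a co-leader (section C).* This applies to the interview. No matching separation is described for the CSQ-8.

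**How large could the effect be?** The documents cannot say. For illustration, take 8 items scored 1-4 and summed:
- Minimum total: 8 × 1 = 8. Maximum: 8 × 4 = 32. Width: 32 − 8 = 24 points.
- If each item is raised by an assumed amount *d*, the mean total rises by 8 × *d*.

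| Assumed *d* per item | Rise in mean total | Share of the 24-point width |
|---|---|---|
| 0.1 | 0.8 | 3.3% |
| 0.25 | 2.0 | 8.3% |
| 0.5 | 4.0 | 16.7% |

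**Could the analysis reveal it?** Write the expected mean as true mean + *b*, where *b* is a shift shared by all parents. Averaging over the target of 12 parents, or over any larger number, leaves *b* unchanged. There is one arm, so no contrast in which *b* would cancel or show itself.

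**The case against.** The strongest reply is that this is a modest issue in a 12-parent pilot that already has sensible safeguards. Responses carry an ID, are entered online and come after treatment. The access statement is made at intake, at least 20 weeks earlier. Acceptability also draws on an exit interview run by someone outside the treating team. The CSQ-8 mean is descriptive, so no stated decision turns on a shift of a few points. The consent form and the CSQ-8 text (Appendices A and U) are not in the supplied documents and may contain an assurance. All of this stands, and it limits the point to a risk of unknown size. It does not remove the point, because nothing in the protocol withholds the CSQ-8 from co-leaders.

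A reader might infer more than the documents support:
- *That the ratings are biased upward by a known amount, or by some number of standard errors.* The per-item shift is assumed and the protocol gives no SD. A standard-error comparison would have no test or threshold behind it.
- *That the independent interviewer shows the authors saw this bias and then overlooked the CSQ-8.* The protocol gives no reason for that choice.
- *That exit-interview material should also be closed to co-leaders.* The PI is a co-leader, has a role in every part of the research and trains those who code the interviews, so that restriction would conflict with the stated roles.
- *That telling parents about access is the fault.* The disclosure is proper. The weakness is that the access disclosed has no exception for the CSQ-8.

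**Conclusion.** The point holds as a risk. The only quantitative acceptability result is collected under a stated expectation that the treating co-leaders can see it. The likely direction of any bias is upward and its size is unknown; the 0.8-4 points shown rest wholly on an assumed 0.1-0.5 points per item and on summed scoring. The planned analysis could not detect or correct such a shift. The exit interview offers a partial qualitative cross-check but cannot repair the mean score.

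The conclusion assumes that assessment data includes the CSQ-8, which is the natural reading of section E with Figure 1, and that the unseen appendices contain no assurance to the contrary. If they do, the protocol should say so. This is a cheap improvement to the plan, not a flaw that undermines the study.

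**What to change.** - In section E, exempt the CSQ-8 from co-leader access.
- Collect the CSQ-8 through a separate Qualtrics link whose responses only the project coordinator can open.
- Release the results to co-leaders, including the PI, only in de-identified or aggregate form and only after all groups have finished.
- Say this in the consent form and in one line at the top of the CSQ-8, since the protection works only if parents know of it.
- Leave access to in-treatment, safety and exit-interview data as it is.

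The project coordinator already sends questionnaire links and handles data collection and storage, so the change amounts to a permission setting and two short pieces of text. The suicidality question on the diary card and the PHQ-9 are separate instruments and are unaffected. The cost is that co-leaders receive no CSQ-8 feedback between groups, which matters somewhat in a project that is still developing its intervention. The exit interviews remain available to them for that purpose.
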